1. A 12-gene biomarker panel (the DCIS Score) derived from the 21-gene Oncotype DX recurrence score has been tested in a subset of patients recruited to ECOG 5194 [44]; this shows good predictive value, with clear discrimination of women who develop subsequent ipsilateral breast events (IBE) from those who do not. In particular, the 10-year risk of invasive IBE was 12% and 19% in women with intermediate and high DCIS scores. This panel has been subsequently validated in a population-based cohort from Ontario, Canada [45]. However, in neither of these studies was it possible to examine the predictive value of the DCIS Score, either for benefit of radiotherapy, or for the use of tamoxifen. Both study populations consisted of patients who did not undergo radiation, and tamoxifen was used by only 25% of E5194 patients. Tamoxifen use data was not available on the Ontario cohort. However, since the DCIS Score was derived from a gene panel that was developed for ER positive invasive breast cancer and includes genes involved in proliferation and estrogen response, there is clear relevance of the DCIS Score to the question of whether or not DCIS patients would benefit from tamoxifen. This is a compelling question, since the uncertainties about the natural history of DCIS and the worries about tamoxifen toxicity conspire to distress women about the value of this medication in terms of overall health. We therefore hypothesize that DCIS Score will relate to tamoxifen benefit, as measured by Ki67 response and mammographic density.
2. Breast tissue and plasma levels of TAM and its metabolites [N-desmethyl tamoxifen (NDT), (E) and (Z) isomers of 4-hydroxytamoxifen (4-OHT), N- desmethyl-4-hydroxytamoxifen (Endoxifen)] are a necessary component of this trial since a key question about transdermal delivery pertains to the ability to achieve effective breast tissue drug concentrations. Although prior data suggest that this is in fact true, the number of samples tested so far is small and testing of multiple samples across the breast has not yet been performed. Therefore, it is important in the present study to measure drug concentrations at a minimum of two locations in women undergoing breast conserving surgery, and more extensively in women undergoing mastectomy.

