### **7.4 Evaluation at Completion of Study Intervention**

#### Study Visit 1: Day of Surgery (following 4-10 weeks of study agent)

- Physical Exam including vitals. The source document for this may be anesthesia or surgery H&P, completed within 14 days prior to surgery.
- BESS questionnaire\*
- Toxicity and AE Assessment\*
- Record Concomitant Medications\*
- Collection of agent and compliance check\* - Capsule count and study gel application
- Clinical Labs – including CBC and Chemistry Panel
- Blood collection for research purposes:

- Two 2.7 mL Blue Top tube (citrate) to obtain plasma for coagulation panel.
- Two 10mL Lavender top tubes (K2EDTA) to obtain plasma and buffy coat or white blood cells (WBCs) for following purposes:
  - a) Plasma for measuring tamoxifen and its metabolites [tamoxifen, *N*-desmethyl tamoxifen, (*E*) 4-OHT, (*Z*) 4-OHT, (*E*) endoxifen, and (*Z*) endoxifen].
  - b) Plasma for measuring steroid hormones (estradiol, progesterone).
  - c) Plasma for measuring IGF-1, IGFBP-3, and SHBG.
  - d) Buffy coat will be saved for DNA/RNA isolation.
- Collection of surgical specimen for drug concentration assay – see section 10 for details.
- Pregnancy Test (only offered for premenopausal women with child-bearing potential).
- Recording of depth of lesion from skin, based on wire localization films in subjects undergoing breast conserving surgery, or on direct measurement during grossing of mastectomy slices in subjects undergoing mastectomy.
- For Premenopausal women, record last menstrual period and estimated next menstrual period dates. Confirm and record actual menstrual period date at Visit 2 or the final phone call.

\*BESS Questionnaire, toxicity and AE assessment, review of concomitant medications, and compliance check (collection and review of study agent) may be performed at either Visit 1 (day of surgery) or on the day prior to surgery.

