#### 10.2.2 Mastectomy sampling procedures (for subjects who opt for mastectomy)

At five sites (Cleveland Clinic, Mayo Clinic, Duke, St Elizabeth, University of Kansas), the drug concentration samples will be harvested by the grossing pathologist as described above in Section 10.2.1. The location of these two samples will be 1) superficial, one centimeter from the superficial surface of the mastectomy specimen, and 2) deep, one centimeter from the deep aspect of the mastectomy specimen. These samples may be taken from the location that is remote to the known location of the DCIS.

At two sites (NU and MSKCC) the mastectomy specimen will be grossed according to the scheme developed for a previous topical gel study, described above and depicted in Figure 2B.

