### **10.3 Shipping Instructions**

### ***10.3.1 Shipping of samples to NU***

All samples on each participant will be sent in a two simultaneous shipments (one frozen shipping with dry ice, and one cold shipping) to NU following Visit 2. This will consist of i) drug assay samples (A and B in Figure 2A or 1-5 in Figure 2B); ii) pre- and post-intervention blood; iii) pre- and post-therapy paraffin blocks or sections of the paraffin block, from institutions that do not allow release of paraffin blocks. The study consent will specifically include permission for hospitals to release blocks to NU. Thus, as each subject completes participation, her samples will arrive at NU in a single batch, minimizing the chances of missing or misplaced samples.

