## 13.4 Primary Objective, Endpoint(s) and Analysis Plan

### 13.4.1 Hypothesis and Primary Objective:

We hypothesize that the application of 4-OHT gel to the breast at a dose of 2 mg per breast daily will result in a decrease in the Ki-67 labeling index of DCIS lesions that is comparable to the decrease seen with use of oral TAM. Further, that this will occur with 4-OHT concentrations in the breast that are significantly higher than circulating levels. The primary objective of this study is to demonstrate that topical transdermal 4-OHT is not inferior to oral tamoxifen in decreasing Ki-67 labeling index (LI) of DCIS lesions. In the control (oral TAM) group we expect the mean relative decrease in Ki-67 LI in the surgical specimen to be 50% compared to the diagnostic core biopsy samples after therapy. In the study agent group we will accept a relative mean decrease of at least 35% as evidence of non-inferiority.

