### 13.5.4 Analysis Plan for Secondary Endpoints:

Secondary outcomes will be summarized by

treatment arm using descriptive statistics, including mean and confidence interval, or median and interquartile range for continuous outcomes, and proportions and confidence intervals for categorical variables. Outcomes will be compared between arms, with two main types of analyses being conducted: noninferiority testing and testing for differences between arms, depending on the specific hypotheses for each outcome. **Noninferiority analyses.** Similar to the primary outcome, we expect changes in secondary efficacy outcomes (Oncotype DCIS-Score) to be similar (noninferior) in the 4-OHT gel arm vs. oral tamoxifen arm. Because preliminary data necessary for setting noninferiority margins are not available for all endpoints, we will use a strategy similar to how the non-inferiority margin was set for the primary endpoint, i.e. we will set the margin  $M$  to correspond to a 35% change from the average baseline value observed among all patients (i.e. pooling across both study arms). These biomarkers will be compared between arms using ANCOVA models similar to those described for the primary endpoint, with post-treatment measurement as the outcome variable, and with treatment arm and baseline value as predictors, and testing  $H_0: \gamma \geq M$  vs.  $H_1: \gamma < M$  as described above. **Treatment differences.** Continuous endpoints for which treatment differences are expected post-treatment (breast and plasma levels of TAM and its metabolites; plasma proteins involved in coagulation; plasma markers of systemic estrogenic effect; and BESS questionnaire) will be compared between arms using a two-sample t-test. Normality assumption will be checked, and data may be transformed (e.g. logarithmically) to satisfy the normality assumption. If no suitable transformation can be found, groups will be compared using the Wilcoxon ranksum test. Additional exploratory analyses will include linear regression models and will adjust for additional covariates. Outcomes for which changes are expected to be different between arms will be analyzed using ANCOVA models as described for the primary endpoint, but testing whether the treatment effect is 0 rather than the non-inferiority margin  $M$ , i.e.  $H_0: \gamma = 0$  vs.  $H_1: \gamma \neq 0$ . These tests will be two-sided. Tests of these pre-specified hypotheses will not be adjusted for multiple comparisons, and will be interpreted accordingly.

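### Tissue drug levels are sampled at two or more locations per woman, but the planned between-arm test has no location term and no rule for a woman's several samples, and the tissue-above-plasma hypothesis has no test

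*Combined protocol and SAP*

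**What the plan says.** - **Why several samples are taken.** Section 2.3.3 (secondary endpoint 2) treats tissue concentrations as essential because the open question for transdermal delivery is whether the breast reaches effective levels. It notes that "testing of multiple samples across the breast has not yet been performed" and concludes that the study should "measure drug concentrations at a minimum of two locations in women undergoing breast conserving surgery, and more extensively in women undergoing mastectomy".
- **Where they are taken.** In breast-conserving surgery the locations are those in Figure 2 (Section 10.2.1), which is not reproduced in the text available. For mastectomy at five sites, Section 10.2.2 states: "The location of these two samples will be 1) superficial, one centimeter from the superficial surface of the mastectomy specimen, and 2) deep". The other two sites use a separate grossing scheme. Section 10.3.1 lists the shipped material as "drug assay samples (A and B in Figure 2A or 1-5 in Figure 2B".
- **Depth.** Section 7.4 includes "Recording of depth of lesion from skin, based on wire localization films", with direct measurement for mastectomy. This is the depth of the lesion.
- **Objective and expectation.** Secondary objective 2 (Section 1.2) is a between-group comparison of post-therapy tissue and plasma levels. Section 13.5.1 expects higher plasma levels in the oral arm and similar tissue levels.
- **Analysis.** Under Section 13.5.4, breast and plasma drug levels "will be compared between arms using a two-sample t-test". Transformation or a rank-sum test is the fallback, and exploratory regressions may add covariates that are not named.
- **Further hypothesis.** Section 13.4.1 adds that "this will occur with 4-OHT concentrations in the breast that are significantly higher than circulating levels".

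**The concern.** The sampling is designed to learn about drug levels at more than one place in the breast. The named tests accept one independent value per woman and contain no location term, so the information that justified the extra samples has no place in the pre-specified analysis. The plan also does not say whether a woman's samples are averaged, one is chosen, or all are entered. These choices lead to different results, and leaving them until the data are in hand invites selection.

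The risk depends on the choice. With averaging, a gel that reaches some locations well and others poorly could have the same arm mean as oral tamoxifen. With pooling, standard errors would be too small and differences could be declared falsely. Separately, the tissue-above-plasma statement in Section 13.4.1 is a comparison within women, and no planned test makes it.

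**Working it through.** **The plan's own figure.** The documents give no power or precision for the tissue endpoint. The only power figure, 80.5% for Ki-67 (Section 13.4.2: 40 per arm, margin 2.6, SD 5.4, one-sided 0.10), reproduces: the non-centrality is 2.6/(5.4 × √(2/40)) = 2.15, and the non-central t with 78 df gives 80.5%. It does not bear on this point.

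**Inputs.** 45 women per arm evaluated for study endpoints (Section 3.2). At least two samples per woman (Section 2.3.3). Labels 1-5 for the two-site mastectomy scheme (Section 10.3.1); reading these as up to five positions is an inference, since the figure is not shown. Two-sided tests (Section 13.5.4). Assumed, because not stated: a 0.05 level for secondary tests and a within-woman correlation ρ of 0.3-0.7.

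**If every sample is entered as independent.** With k samples per woman the design effect is DE = 1 + (k − 1)ρ. The standard error is understated by 1 − 1/√DE, and the true two-sided error is 2 × [1 − Φ(1.96/√DE)]. For k = 2:

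| ρ | DE | SE understated by | True error | Simulated (45 per arm) |
|---|---|---|---|---|
| 0.3 | 1.3 | 12% | 8.6% | 9.0% |
| 0.5 | 1.5 | 18% | 11.0% | 11.3% |
| 0.7 | 1.7 | 23% | 13.3% | 14.2% |

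At ρ = 0.7, 90 samples per arm carry the information of 90/1.7 = 53 independent ones. If every woman gave five samples, DE would be 2.2-3.8 and the error 18.6-31.5%, but that scheme covers only mastectomies at two of seven sites. With an assumed mix in each arm of 36 women giving two samples and 9 giving five, simulation gave 12.3%, 17.8% and 21.5% at ρ = 0.3, 0.5 and 0.7.

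**If one mean per woman is used.** Simulated error was 4.5-5.4% across the same settings, so the nominal level holds. Location is lost, however. As an invented illustration, gel levels of 9 and 1.8 ng/g at two locations average (9 + 1.8)/2 = 5.4 ng/g, the oral-arm mean in the previous DCIS trial (Section 2.3.2).

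**What a within-woman contrast could detect.** At 80% power and two-sided 0.05, the detectable paired difference between two locations, in single-sample SDs, is 2.80 × √(2(1 − ρ))/√n. For the arm-by-location interaction, multiply by √2.

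| Women per arm with both samples | Paired difference, ρ = 0.3 / 0.5 / 0.7 | Interaction, ρ = 0.3 / 0.5 / 0.7 |
|---|---|---|
| 45 | 0.49 / 0.42 / 0.32 | 0.70 / 0.59 / 0.46 |
| 10 (assumed) | 1.05 / 0.89 / 0.69 | 1.48 / 1.25 / 0.97 |

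**Tissue versus plasma.** Section 13.4.1 needs tissue and plasma from the same woman, which Section 3.7 requires on the same day. All drug-level tests in Section 13.5.4 set gel against oral. None sets tissue against plasma.

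**The case against.** The strongest reply is that the worded objective is analysed. Objective 2 asks for a between-arm comparison, Section 13.5.4 supplies one, and Section 2.3.3 gives a reason to measure at several places without stating a hypothesis about depth. That stands: the gap is between the sampling rationale and the analysis, and it is not an objective left untested.

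Second, a two-sample t-test is naturally read as one value per woman, and then the error rate is correct. That also stands. A reader might infer that the plan commits to an inflated test; it does not. The 9-13% needs both pooling, which the plan does not state, and a correlation that the documents do not give. Pooling would also tend to produce false differences, contrary to the expected similarity, so it would not favour the gel. The 19-31% for five samples is not a trial-level figure. Nor does site-dependent sampling by itself bias the arm comparison, because randomisation is blocked within site.

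Third, a reader might infer that superficial and deep samples exist for every woman, or that the recorded depth supplies them. The text confirms those labels only for mastectomies at five sites. Section 7.4 records lesion depth, and Section 10.2.2 allows samples remote from the lesion. The previous trial's gel-arm spread (5.8 ± 9.3 ng/g) shows wide variation, not a depth gradient.

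Fourth, the tissue-plasma test may be close to a formality: the earlier gel arm had 5.8 ng/g in tissue and 0.2 ng/mL in plasma. Even so, a hypothesis worded as a significant difference should have a named test.

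The exploratory regressions do not close the gap, since they name neither location nor a woman-level effect. The authors do specify a subject random effect elsewhere, for Ki67 mRNA and IHC in Section 13.5.5.

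**Conclusion.** The concern holds as a gap between why the samples are taken and how they are analysed. Following Section 13.5.4 either discards location (one mean per woman, nominal error kept) or treats correlated samples as independent (about 9-13% for a nominal 5% with two samples per woman and assumed correlation 0.3-0.7, higher where some women give up to five). The plan does not say which. The tissue-above-plasma hypothesis in Section 13.4.1 has no planned test; that part rests on no assumed figure.

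The documents do not support the stronger conclusions that type I error is inflated as planned, that a worded objective goes unanalysed, or that a superficial-to-deep contrast is available in all women. This is a secondary endpoint and the primary analysis is unaffected, but the change should be made before the concentrations are seen.

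**What to change.** In Section 13.5.4:

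1. Replace the t-test for tissue levels with a linear mixed model on log concentration: random intercept for woman; fixed effects for arm, sample location and arm-by-location.
2. Report the gel/oral ratio with confidence interval overall and by location. Use superficial and deep labels only where the sampling scheme defines them. Ratios with intervals also suit the expectation of similar tissue levels better than a non-significant difference test.
3. Adjust for operation type only as a sensitivity analysis, because the documents do not say it is fixed before randomisation.
4. Add a within-woman comparison of log tissue with log plasma 4-OHT in the gel arm for the Section 13.4.1 hypothesis, stating how ng/g and ng/mL are equated.

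The cost is SAP wording and a little more analysis; the tissue samples and same-day plasma are already planned. Location-specific intervals will be wider than for one pooled mean. If few women have defined depths, the interaction will be imprecise: with 10 per arm (assumed), only 0.97-1.48 SD would be detectable at correlation 0.3-0.7.

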3. Ki67 labeling index in terminal duct lobular units (TDLUs) will be evaluated in the same manner as the primary endpoint (KI67 LI in the DCIS lesions). We expect 10 to 20 percent of participants would have no residual DCIS in the surgical samples and they cannot be included in the main analysis for the primary endpoint since Ki67 in DCIS at both time points is required for that purpose. However, TDLUs are present in most tissue sections. Existing data suggest that breast cancer risk is higher in women whose TDLUs show increased Ki67 LI[47, 48], and is reduced by short-term tamoxifen use, even at lower doses[49, 50]. Therefore, we have now included a secondary endpoint of Ki67 reduction in TDLUs, to be compared in both arms, and we expect that changes in TDLU Ki67 LI will be non-inferior in the gel arm.
4. As secondary endpoints related to toxicity, we have identified three areas for measurement: a) Plasma proteins involved in coagulation: Factors VIII and IX, von Willebrand Factor, total Protein S. We expect that the oral tamoxifen group will show significant changes and the 4-OHT gel group will not. B) Plasma markers of systemic estrogenic effect (IGF-1, IGFBP-3, and SHBG); we expect that these will change in the oral tamoxifen group but not in the 4-OHT gel group. C) Symptoms as captured in the BESS questionnaire and skin reactions to 4-OHT gel. We expect that symptoms will be less severe in the 4-OHT gel group, and skin toxicity will be minor or none.

Exploratory endpoints:

1. Other immunohistochemical (IHC) markers have been investigated in a DCIS cohort in California; Tlsty and colleagues have identified Ki67, COX2, and p16 expression as predictors of invasive recurrence [46]. In a different, presurgical endocrine therapy study, Hwang and colleagues have identified CD-68 (a macrophage marker) as a surrogate for DCIS response to endocrine therapy. We hypothesize that this panel of markers will complement the evaluation of Ki67 response, and aid interpretation of responses that fall at the extremes (excellent or no change in Ki67).

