### 13.4.2 Proposed Sample Size:

A total of up to 108 women will be accrued and randomized over an 18 month period (1:1 oral:gel), with no more than 100 women to start intervention. Assuming a 20% rate of nonevaluable samples due to insufficient residual DCIS, we expect a total of 80 subjects evaluable for the primary endpoint of Ki67, comparing pre to post-therapy samples. Primary analysis will be conducted in all randomized evaluable patients per intent-to-treat. Additional analyses will be conducted in the per-protocol population of patients who were treatment-compliant as defined in Section 5.7. Adverse events will be evaluated in all patients who received at least one treatment dose.

Sample size calculations: From previous publication (Table 2, Lee et al.) we have an average percent staining for Ki67 at baseline of 7.5% with  $SD=5.4\%$ . Assuming within-subject correlation between pre- and post-treatment values is  $\rho=0.5$ , the pooled  $SD$  of the changes will be  $SD_p=5.4\%$ . A 50% drop (from 7.5%) gives 3.75% while a 35% drop (from 7.5%) gives 4.9% in Ki67 staining. If the drop in the 4-OHT group is non-inferior to the standard of care, we would see it. We use compatible  $SD$  from Table 2 in Lee et al, obtaining for the 4-OHT group adequate power to detect a non-inferiority of 35% or bigger drop with a small type 1 error of 10%. Now 2.6% staining. Thus, with a non-inferiority margin  $M=2.6\%$ , sample size of  $n=40$  evaluable patients per arm will provide 80.5% power with one-sided  $\alpha = 0.10$  significance level to detect non-inferiority based on a two-sample equal variance t-test comparing changes in Ki67% staining. Calculations were done using PASS 11.

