### 13.4.3 Statistical analysis plan for primary endpoint:

The primary objective is to estimate and compare changes in %Ki-67 expression from the pre-treatment specimen to the post-treatment specimen between women who received oral Tamoxifen + placebo gel compared with those who receive 4-OHT gel + oral placebo. When using a continuous outcome measured at baseline and after treatment in a randomized trial, it is recommended to use an analysis of covariance (ANCOVA) to model[55, 56]). In addition, the two-sample t-test comparing the change score  $Y_1 - Y_0$  vs.

treatment is prone to incorrect interpretations if the correlation between  $Y_1$  and  $Y_0$  is high, and the ANCOVA model is preferred in this instance.

In this study, we will use the model  $Y_1 = \alpha + \beta Y_0 + \gamma G + \epsilon$ , where  $Y_1$  and  $Y_0$  are the post- and pre-treatment %Ki-67 expression, and  $G = 0$  or  $1$  indicates whether the subject belongs to the treatment (4-OHT) or the active control group. This model will be used to test whether the difference between treatment arms ( $\gamma$ ) exceeds the pre-specified non-inferiority margin by testing  $H_0: \gamma \geq M$  v.s.  $H_1: \gamma < M$ , where  $M=2.6\%$  is the pre-specified non-inferiority margin. In order to perform such test, we will modify the outcome as  $Y_1^* = Y_1 - M$  when  $G = 1$ , or  $Y_1^* = Y_1$  otherwise. Thus, the model becomes  $Y_1^* = \alpha + \beta Y_0 + \gamma^* G$ , and  $\gamma^* = \gamma - M$ . This corresponds to the hypothesis tests  $H_0: \gamma^* \geq 0$  v.s.  $H_1: \gamma^* < 0$ , which can be obtained from the standard regression model output in a software package. The model will also adjust for the stratification variable menopausal status. The above-described ANCOVA model is different from the non-inferiority test used for the power analysis; however, the power for the ANCOVA models is likely to be greater than power for a t-test comparing change scores [57]. %Ki-67 expression may be transformed (e.g. using log-transformation) to satisfy the normality assumption.

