**13.5.5 Analysis Plan for Exploratory Analyses.** Exploratory endpoints will be analyzed similarly to the primary and secondary endpoint analysis, driven by the hypotheses regarding treatment differences or between arms. In an additional exploratory analysis we will examine correlation between mRNA Ki67 expression and Ki67 IHC staining in a subset of study participants with both assays. Graphical tools will be used and data will be summarized using a correlation coefficient. Linear regression models with ki67 IHC assay as the outcome and mRNA ki67 assay as the predictor may be used to further examine the relationship, e.g. if the association appears nonlinear. Linear mixed effects models may also be used if paired assays are performed at both pre- and post-treatment, and will include subject as the random effect to account for the within-subject correlation between the two time points. This analysis will guide planning of future trials and is not intended as a formal endpoint for the present trial.

**Pathologic response:** Another endpoint of interest is the evaluation of pathologic response, complete (no residual DCIS in the surgical sample). If there is no residual DCIS in the surgical sample, this could mean that the DCIS was small enough at diagnosis that it was ablated by the core needle biopsy; or that the residual DCIS responded completely to therapy. With our present design it is not possible to distinguish between these two possibilities, but we will explore the possibility of pathologic complete response (pCR) in the following ways: the rate of “no residual DCIS” in clinical series and in our institution is about 10%. If we observe that the rate of no residual DCIS is doubled to 20%, we will take this as preliminary evidence of pCR.

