### 13.6 Reporting and Exclusions

**Reporting and Exclusions:** We expect that 80 subjects will have complete data on the primary endpoint, while about 28 subjects out of 108 (roughly 25%) will be excluded because of not starting study medication, study drop-out, or insufficient DCIS in the surgical specimen. Main analysis will be based on the complete data. Additional descriptive analysis may be performed to see if drop-outs show a systematic property. Thus, we expect the 20% of data missing values will be studied to determine possible patterns and dependence with other relevant variables.

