### 13.8 Evaluation of Response

13.8.1 *Intent to treat analysis* All samples from all subjects who receive drug will be evaluated and included in the primary analysis, which will be based on intent to treat principle. Per protocol analyses will then be performed as described in Section 8.4.2.

13.8.2 *Missing data* The general approach will be to perform a complete case analysis when the missingness rate is low, and when a missing completely at random (MCAR) or missing at random (MAR) assumption can be reasonably made. To determine whether such assumptions are reasonable, reasons for data missingness will be documented, and clinical and demographic characteristics will be compared between patients with and without missing data for each particular endpoint. If the missing data rate is relatively high but the MAR assumption is reasonable, complete case analyses will be done and carefully interpreted given high missing data rates. To assess the robustness of findings, sensitivity analyses will be performed, including covariate-adjusted regression models, and “best-worst” analyses where all missing values are replaced by either best or worst values for categorical outcomes, and by highest or lowest observed values for continuous outcomes. Multiple Imputation. If data is missing for > 10% of the entries, multiple imputation may be performed via a semiparametric approach based on association between continuous biomarker variables, between binary variables, and between continuous with binary and categorical data [see refs 52-55]. In these approaches, missing data are filled in by plausible values obtained from joint modeling. Observed data are first transformed to normally distributed values so as to satisfy the normality assumptions of the joint modeling approach. Imputed data are then transformed back onto the original scale of the observed data. Imputations are run until convergence criteria are met depending on pairwise correlations between the variables imputed. Performance of the multiple imputation will be assessed via standardized biases (< 50% being acceptable), coverage rates (> 90% being acceptable), small root mean square errors, and average widths of 95% confidence intervals for the estimates from imputed data being comparable to the widths of 95% confidence intervals for the original data pertaining to the pairwise correlations. The goal for the imputed data is to satisfy the assumptions from our power analysis and ensure the convergence of parameter estimation.

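### Women with no residual DCIS are left out of the primary analysis and handled like any other missing data, although the plan says they may be complete responders; unequal clearance between arms could bias the comparison toward non-inferiority

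*Combined protocol and SAP*

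**What the plan says.** - **Exclusion.** Section 2.3.3 (secondary endpoint 3) expects 10 to 20% of participants to have no residual DCIS and says "they cannot be included in the main analysis for the primary endpoint since Ki67 in DCIS at both time points is required". It adds Ki-67 in terminal duct lobular units (TDLUs) as a secondary endpoint for this reason.
- **Meaning of an absent lesion.** Section 2.3.3 (exploratory endpoint 3) gives a background rate of about 10% and would read a rate above 20% across both arms as drug-related regression. Section 13.5.5 says the lesion may have been removed by the biopsy, "or that the residual DCIS responded completely to therapy", and that this design cannot tell the two apart.
- **Analysis set.** Section 13.6 counts insufficient DCIS together with not starting medication and drop-out. It then says: "Main analysis will be based on the complete data".
- **Missing data.** Section 13.8.2 uses complete cases when missingness is low and MCAR or MAR can reasonably be assumed. For higher rates: "If the missing data rate is relatively high but the MAR assumption is reasonable, complete case analyses will be done". It adds covariate-adjusted models and replacement of missing values by the highest or lowest observed value. Multiple imputation is optional above 10% missing. It has no rule for women with no residual DCIS and no primary approach if MAR is judged unreasonable.
- **Label.** Sections 8.4.2, 13.4.2 and 13.8.1 call the primary analysis intent-to-treat.

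**The concern.** By the plan's own account, whether a woman has a post-treatment DCIS Ki-67 may depend on how well her treatment worked. Restricting the analysis to women who still have DCIS then selects on an outcome that arises after randomization. If the control drug clears more lesions, its best responders leave the control mean and the gel is compared with a less favourable remainder. In a non-inferiority trial that favours the new product.

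The imputation option adds a separate problem. The plan expects 20 of 100 starters to lack primary data, so the 10% trigger is likely to be met. Imputation would then generate a DCIS Ki-67 for lesions that are no longer there.

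**Working it through.** **Inputs from the documents.** Section 13.4.2: "average percent staining for Ki67 at baseline of 7.5"%, SD 5.4, pre-post correlation 0.5, expected oral post-treatment mean 3.75, a "small type 1 error of 10"% and one-sided testing. Margin M = 2.6 points (13.4.2, 13.4.3). Section 3.2: 45 women per arm with endpoint data, 40 per arm with primary data.

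**1. The plan's own figure.** SD of change = √(2 × 5.4² × (1 − 0.5)) = 5.4. With 40 per arm, SE = 5.4 × √(2/40) = 1.207 and M/SE = 2.153. Assuming a true difference of 0, the noncentral t gives 80.52% power. The plan says 40 "evaluable patients per arm will provide 80.5% power with one-sided" α = 0.10. It reproduces, so the sample-size figure is not at fault.

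**2. Size of the shift.** Assume that women with residual DCIS have the same mean (3.75) in both arms and that a cleared lesion counts as 0. The complete-case difference (gel minus oral) is 0. Counting everyone:

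| No residual, gel / oral | Difference over all women | Share of M |
|---|---|---|
| 10% / 10% | 0.90×3.75 − 0.90×3.75 = 0 | 0 |
| 10% / 15% | 0.90×3.75 − 0.85×3.75 = 0.19 | 7% |
| 10% / 20% | 0.90×3.75 − 0.80×3.75 = 0.375 | 14% |
| 10% / 30% | 0.90×3.75 − 0.70×3.75 = 0.75 | 29% |

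**3. Chance of passing when the all-women difference equals M.** The gel mean among women with residual DCIS is (2.6 + (1 − p_oral) × 3.75)/(1 − p_gel), and d is that mean minus 3.75. Pass probability ≈ Φ((2.6 − d)/SE − 1.2816). The ANCOVA residual SD is 5.4 × √(1 − 0.5²) = 4.68, with 45 women per arm before removal.

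- 10% / 10%: d = 2.889, SE = 1.039, pass 5.9%.
- 10% / 15%: d = 2.681, SE = 1.054, pass 8.7%.
- 10% / 20%: d = 2.472, SE = 1.071, pass 12.3%.
- 10% / 30%: d = 2.056, SE = 1.111, pass 21.4%.

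With the change-score SD of 5.4 the last two are 11.9% and 19.6%. Simulating the ANCOVA without the menopausal term gives 12.1% and 20.8%.

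**4. A harsher assumption.** Suppose an extra 10% of oral women are lost because their Ki-67 would have been low, on top of 10% random loss in both arms, and the true difference is 2.6. Simulation gives a mean estimate of 2.28 and a 16% pass rate if they come at random from the lower half, or 1.87 and 29% if they are the very lowest. The documents do not say how strong such selection would be.

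**5. Do the planned checks isolate it?** Take 10% random drop-out in both arms and a lowest observed value near 0.

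- Replacing all missing values by the lowest, with 10% / 20% no residual: 0.9×0.9×3.75 − 0.9×0.8×3.75 = 0.34. The signal appears.
- With equal 10% no-residual rates and 10% / 20% drop-out instead: 0.9×0.9×3.75 − 0.8×0.9×3.75 = 0.34. The result is identical, so the check cannot tell clearance from drop-out.
- The exploratory comparison of no-residual fractions has 26 to 29% power for 10% against 20% with 45 to 50 per arm (normal approximation, two-sided 5%), or 18 to 19% with Fisher's exact test.
- The 20% trigger is pooled: 10% and 20% average 15%.

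**6. Would scoring zero in both arms at the same margin repair it?** Suppose biopsy alone clears the same share in each arm and the difference among residual lesions equals M (6.35 against 3.75). At 10% per arm the composite difference is 0.9 × 2.6 = 2.34, SE ≈ 1.006, and the pass rate is Φ(0.26/1.006 − 1.2816) = 15.3%. At 20% it is 2.08, SE ≈ 1.011, 22.1%. Simulation gives 15.1% and 22.4%. That inflates false non-inferiority about as much as the bias it is meant to expose.

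**The case against.** A reader might infer that the plan simply assumes these women are MAR. It does not. Section 13.8.2 makes complete-case analysis conditional on that assumption being reasonable, documents reasons for missingness, and compares women with and without data. Multiple imputation is optional.

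A reader might also infer that no planned analysis could reveal the problem. That is too strong: lowest-value replacement would pick up most of the shift in step 5, and the no-residual fraction is compared between arms. What remains is that neither isolates these women from drop-outs, and neither is linked to the primary conclusion.

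The strongest reading is that the exclusion would make the gel look non-inferior. The documents do not support it. They give no by-arm rates, Section 13.5.3 expects similar fractions, and about 10% have no residual lesion without any drug effect. With equal rates, or 10% against 15%, the pass rate under zero scoring stays below 10%. Calling the excess an error also presupposes that a cleared lesion should count as zero, whereas the stated endpoint is Ki-67 in DCIS lesions. This is also a Phase IIB biomarker trial tested at 10%.

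These points limit the size and certainty of the bias. They do not supply the missing rule, or a reason to impute Ki-67 where there is no DCIS.

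**Conclusion.** The concern stands as a gap in the analysis plan with a possible bias, not a demonstrated one. The plan treats absence of residual DCIS as possible drug effect in one place and as ordinary missing data in another. The bias arises only if clearance differs by arm, and it runs toward non-inferiority if oral tamoxifen clears more. Under zero scoring it is modest at 20% against 10% (0.375 points, about 12% instead of 10%) and material at 30% against 10% (0.75 points, about 21%). Strong selective loss of low-Ki-67 oral lesions would make it larger. The by-arm rates, the zero score and the degree of selection are all assumptions. The intent-to-treat label claims more than this analysis set can deliver.

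**What to change.** In Sections 13.6 and 13.8.2:

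1. Report primary-endpoint losses by arm and by reason, separating no residual DCIS from drop-out and from insufficient tissue.
2. Do not impute DCIS Ki-67 where there is no residual DCIS; limit imputation to data that are truly missing.
3. Keep the complete-case ANCOVA as primary, but describe it as an analysis of women with residual DCIS and not as full intent-to-treat. Align 8.4.2, 13.4.2 and 13.8.1.
4. Pre-specify a supportive sensitivity analysis for no-residual women only: a by-arm tipping-point analysis that includes the case where only the excess no-residual fraction in the oral arm is scored as the best outcome (zero or lowest observed value), plus a rank-based composite.

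Do not make a zero-score composite in both arms at the 2.6-point margin a condition for calling the result robust, for the reason in step 6 of the working. Zero also has no logarithm, and Section 13.4.3 allows a log transformation, so the scale of the scoring must be stated.

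The cost is SAP wording and a few extra analyses. The study pathologist already assesses residual DCIS (Section 8.2.10), so no new data are needed. The downside is that the conclusion may need qualifying if no-residual rates differ by arm.
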